12.4 Exploratory/Ancillary Correlative Studies

Monitoring Peripheral Blood for Changes in Immune Function and Angiogenic Factors

Correlative sciences will be expanded from the previous determined biology and analyses developed through our experience thus far with ipilimumab and ipilimumab-bevacizumab treated patients. Subpopulations of PBMCs will be isolated, including but not limited to dendritic cells, T cells, and B cells. Phenotype changes in these cell populations by flow cytometry will be determined as a function of treatment. These include regulatory and effector immune panels, naïve and memory CD4, CD8 and NK lymphocyte populations. Given its importance in immune regulation and association, we will evaluate Tie-2 expressing monocytes (TEM). Changes in antigen specific responses to known tumor associated antigen epitopes (MART-1, NY-ESO-1) will be determined utilizing HLA-A20201 peptide system for APC (including DC maturation and presentation) and targets.

Both humoral and cellular immune responses will be investigated by ELISAs, ELISPOTs, and cytotoxic T cell chromium release assays. We will investigate the effects on tumor vasculature and vascular active molecules as a function of treatment with the two-drug combination. We have recently reported that pre-treatment serum VEGF levels predict clinical benefit to ipilimumab (Yuan, Zhou et al. 2014). We will therefore investigate angiogenic cytokines pretreatment levels as well as changes in levels as a function of treatment. Studies will include monitoring VEGF, bFGF, and HGF levels. Circulating endothelial cells and progenitors will be studied as a function of treatment.

For the analysis of cytokines, chemokines, and immune cell populations from serum or blood, data will be combined from all four diseases, resulting in longitudinal measurements for 48 patients. Serum marker levels will be summarized descriptively and graphically. The time course of expression levels will also be summarized graphically by patient, noting disease group and times of disease progression.

12.5 Sites Performing Correlative Study

[REDACTED]

13. DATA REPORTING / REGULATORY REQUIREMENTS

Adverse event lists, guidelines, and instructions for AE reporting can be found in Section 7.0 (Adverse Events: List and Reporting Requirements).

13.1 Data Reporting

13.1.1 Method

The Office of Data Quality (ODQ) will collect, manage, and perform quality checks on the data for this study.

13.1.2 Responsibility for Data Submission

Investigative sites within DF/HCC or DF/PCC are responsible for submitting data and/or data forms to the Office of Data Quality in accordance with DF/HCC SOPs.

13.2 Data Safety Monitoring

The DF/HCC Data and Safety Monitoring Committee (DSMC) will review and monitor toxicity and accrual data from this study. The committee is composed of clinical specialists with experience in oncology and who have no direct relationship with the study. Information that raises any questions about participant safety will be addressed with the Overall PI and study team.

The DSMC will review each protocol up to four times a year or more often if required to review toxicity and accrual data. Information to be provided to the committee may include: up-to-date

participant accrual; current dose level information; DLT information; all grade 2 or higher unexpected adverse events that have been reported; summary of all deaths occurring within 30 days of intervention for Phase I or II protocols; for gene therapy protocols, summary of all deaths while being treated and during active follow-up; any response information; audit results, and a summary provided by the study team. Other information (e.g. scans, laboratory values) will be provided upon request.

14. STATISTICAL CONSIDERATIONS

14.1 Study Design/Endpoints

This protocol is a phase Ib trial to assess the safety and tolerability of the combination of pembrolizumab with trebananib, determine the recommended dosing, and to obtain preliminary estimates of efficacy. Dose-finding will be based on a standard 3+3, dose escalation design conducted in patients with solid tumors (Section 2.1). After a recommended dose has been determined from the dose escalation, a dose expansion study will be conducted in three cohorts of patients: ovarian, renal, or colorectal cancer. For ovarian cancer 12 patients will be enrolled and treated. For CRC patients total of 37 patients will be enrolled on the expansion cohort. For the RCC cohort only 4 patients will be enrolled on the expansion cohort.

Safety assessments will include all patients receiving one or more doses of either of the study drugs. Secondary and correlative endpoints will be based on the cohorts of patients enrolled in the dose expansion portion of the trial, and may include those patients in the dose escalation who received the recommended dose and had the same tumor type. We will summarize secondary and correlative endpoints according to disease indication and, in an exploratory fashion, with all patients combined.

14.2 Sample Size, Accrual Rate and Study Duration

Dose Escalation: The dose escalation portion of the trial will enroll between 6 and 12 patients. The minimum would occur if dose cohorts 1 and -1 stop due to excess toxicity after the first three patients in each are assessed for DLT. The maximum is based on two cohorts of 6 patients each. Patients in any dose escalation cohort who cease treatment during the DLT assessment window due to rapid progression of disease will not be counted as having a DLT, and may be replaced.

Dose Expansion: Total sample size will be 53 evaluable patients. The same criteria used to define evaluable patients for objective response in section 14.5 should be used here.

Patients with melanoma, ovarian cancer, colorectal cancer or renal cancer who receive the recommended dose in the dose escalation will be included in the dose expansion analyses.

We will close the melanoma cohort and stop enrolling on the current RCC cohort after 4 patients have been enrolled due to low accrual rate. We will continue enrolling ovarian cancer patients on the ovarian expansion cohort as planned up to 12 patients.

We performed an interim analysis of the 15 CRC patients who received the RP2D (3 in the dose escalation and 12 in the dose expansion) and observed a response rate of 7% (1 PR), 4 patients (26%) with best RECIST response of stable disease for a median of 10 months, and median OS of 9 months. The disease control rate (DCR), defined as best RECIST response of complete or partial response or stable disease of at least 6 months duration, was 33%. Since this activity exceeds the historical control in patients who were heavily pre-treated with chemotherapy (DCR 15%, median OS 5 months) (Grothey, Lancet. 2013 Jan 26;381(9863):303-12) we decided to expand the CRC cohort by adding 25 patients. We will expand the CRC cohort with a target sample size of 40 patients (15 already enrolled plus 25 additional) to assess the DCR in these patients. This will be a single-stage design that will have 85% power to detect a difference in DCR of 15% versus 30% with a one-sided $\alpha=0.1$ using a chi-squared test. The null DCR of 15% will be rejected if there are 9 or more patients with disease control out of 40 CRC patients. For analysis, we will present the DCR with a one-sided 90% exact confidence interval.

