3.1 Eligibility Criteria

In order to be eligible for participation in this trial, the participant must meet the following criteria on screening examination:

- 3.1.1** Be willing and able to provide written informed consent for the trial.
- 3.1.2** Be ≥ 18 years of age on day of signing informed consent.
- 3.1.3** Have measurable disease based on RECIST 1.1.
- 3.1.4** In dose escalation (Phase I), patients must have histologically or cytologically confirmed metastatic disease from any solid tumor that is incurable and fulfills one of the following criteria:
 - a) Has demonstrated progression of disease following at least one line of effective systemic therapy. Prior treatment with anti-CTLA-4 antibody (including ipilimumab) is allowable
 - OR
 - b) For which effective therapy does not exist
- 3.1.5** In dose expansion (part 2), patients must have histologically or cytologically confirmed unresectable or metastatic melanoma, renal cell carcinoma, ovarian cancer, or colorectal cancer.
- 3.1.6** Renal cell patients must have had at least one prior VEGF TKI.
- 3.1.7** Ovarian cancer patients must be resistant to platinum therapy (i.e. within 6 months of last platinum therapy).
- 3.1.8** Patients with colorectal cancer should have progressed on at least one fluorouracil plus irinotecan or oxaliplatin containing regimen.
- 3.1.9** Patients with melanoma should have unresectable or metastatic disease. Melanoma patients with BRAF V600E or V600K mutation-positive melanoma who have previously received a BRAF inhibitor with or without a MEK inhibitor) are eligible.
- 3.1.10** In the dose expansion cohort patients should be willing to provide tissue from a newly obtained core or excisional biopsy of a tumor lesion (pre-treatment) and an on-treatment biopsy. Newly-obtained is defined as a specimen obtained up to 6 weeks (42 days) prior to initiation of treatment on Day 1. Patients for whom newly-obtained samples cannot be provided (e.g., inaccessible, participant safety concern, or unwilling to undergo biopsy) may submit an archived specimen only upon agreement from the Sponsor. An on-treatment biopsy will be collected approximately halfway through the induction period, about 6 weeks from the start of study treatment (sometime between Cycle 2 Day 8– Cycle 3 Day 1).
- 3.1.11** Have a performance status of 0 or 1 on the ECOG Performance Scale (see Appendix A) up to 28 days before treatment initiation

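### The 15% null DCR comes from heavily pre-treated patients, but CRC patients can enter after one regimen, so rejection in all 40 does not by itself show activity above the historical rate for the patients enrolled

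*Combined protocol and SAP*

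**What the plan says.** Section 14.2 reports an interim look at 15 CRC patients treated at the RP2D, 3 from escalation and 12 from expansion. Disease control, "defined as best RECIST response of complete or partial response or stable disease of at least 6 months duration, was 33"%, is compared with a cited published control: "Since this activity exceeds the historical control in patients who were heavily pre-treated with chemotherapy (DCR 15%, median OS 5 months"). Median OS in the 15 patients was 9 months.

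The cohort was then enlarged to a "target sample size of 40 patients (15 already enrolled plus 25 additional) to assess the DCR in these patients". The test is specified as follows: "This will be a single-stage design that will have 85% power to detect a difference in DCR of 15% versus 30"%, one-sided at 0.1, and "The null DCR of 15% will be rejected if there are 9 or more patients with disease control out of 40 CRC patients".

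Eligibility for CRC in expansion (3.1.8) reads: "Patients with colorectal cancer should have progressed on at least one fluorouracil plus irinotecan or oxaliplatin containing regimen". The three escalation patients entered under 3.1.4, whose first route is "Has demonstrated progression of disease following at least one line of effective systemic therapy" and whose second is that no effective therapy exists. Neither criterion sets a minimum above one prior line.

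Section 5.8 rules out stratification. Section 14.3 summarises disease characteristics descriptively. Neither 14.2 nor 14.6 splits or adjusts the DCR analysis by prior lines. Section 10.3.1.1 has all prior cancer treatments reviewed for every participant.

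**The concern.** With no control arm, the historical value is the whole comparison. What a rejection means depends on whether 15% is the DCR that the enrolled patients would have had without the study combination. The plan describes the source of the 15% as heavily pre-treated, while its own entry rule reaches down to one prior regimen. If patients with fewer prior regimens have a higher background DCR, each one enrolled raises the rate expected with no added activity, while the null stays at 15%. The test can then reject partly because of who was enrolled.

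This is the only efficacy endpoint in the plan with a null, an alpha, a power and a rejection rule. The same control was the reason for adding 25 patients. The comparison of 9 with 5 months' OS has the same weakness.

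**Working it through.** **Inputs from the plan (14.2).** N = 40; null DCR p0 = 0.15; alternative p1 = 0.30; one-sided alpha 0.10; reject at 9 or more; stated power 85%.

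**Step 1: reproduce the plan's figure.** One-sample score (chi-squared) test, normal approximation, no continuity correction:

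- Critical proportion = p0 + 1.2816 × √(p0(1 − p0)/40) = 0.15 + 1.2816 × √(0.1275/40) = 0.15 + 1.2816 × 0.05646 = 0.2224.
- Critical count = 40 × 0.2224 = 8.89, so 9 or more.
- Power = Φ((0.30 − 0.2224)/√(0.21/40)) = Φ(0.0776/0.07246) = 85.8%.

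The cut-off and the stated power both reproduce.

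**Step 2: set the right baseline.** The exact binomial chance of 9 or more of 40 at a true DCR of 15% is 13.5%. This is the figure to measure case mix against, not the nominal 10%, because the gap between 10% and 13.5% comes from the cut-off alone. With 10 or more as the rule, the exact figure is 6.7%.

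**Step 3: add case mix (assumptions).** The documents give no prior-line counts for CRC patients and no DCR by line. Suppose n1 of the 40 have a background DCR of d1 and the rest 15%, with no added activity from the combination. The count with disease control is then Bin(n1, d1) + Bin(40 − n1, 0.15), and the mean DCR is [n1 × d1 + (40 − n1) × 0.15]/40.

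| Share less pre-treated | d1 | Mean background DCR | P(9 or more) | P(10 or more) |
|---|---|---|---|---|
| None | – | 15% | 13.5% | 6.7% |
| Quarter (n1 = 10) | 20% | 16.25% | 19% | 10% |
| Quarter | 25% | 17.5% | 26% | 15% |
| Quarter | 30% | 18.75% | 33% | 20% |
| Half (n1 = 20) | 20% | 17.5% | 26% | 15% |
| Half | 25% | 20% | 41% | 27% |
| Half | 30% | 22.5% | 56% | 41% |

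**Step 4: separate the two sources.** The last column shows what an exact cut-off would and would not repair. At a quarter share with d1 = 20% it brings the chance of rejection to about the nominal 10%. At a half share with d1 = 25% the chance is still 27%. The cut-off therefore accounts for part of each figure, and case mix can account for the rest.

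**The case against.** The strongest reply is that a mismatch is possible but not shown. Criterion 3.1.8 is a floor, not a description of who was enrolled. After naming the heavily pre-treated control, 14.2 says the expansion will assess DCR in these patients, so the investigators may have regarded their cohort as comparable. This stands: the documents cannot settle the enrolled mix, and the shares and background rates above are assumptions. That less pre-treated patients have a higher background DCR is also an assumption, although a reasonable one.

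A reader might infer that even a modest share of less pre-treated patients makes a false rejection likely. The figures do not support that. A quarter share gives 19% to 33%, and only one of the six scenarios passes 50%. That scenario gives half the cohort a background DCR of 30%, which is the design's own alternative.

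A reader might also conclude that the 40-patient test should be replaced by one in matched patients only. The case for that is weak. With 20 matched patients the exact rule is 6 or more (alpha 0.067), with power 58% at a DCR of 30%. The subset would be chosen after 15 outcomes are known. The documents describe the control only as heavily pre-treated with chemotherapy and do not state its entry requirement.

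Finally, efficacy here is secondary and preliminary, 14.6 calls within-disease analyses primarily descriptive, and no decision is tied to rejection. This lowers the stakes. It does not remove the point, because 14.2 keeps a formal rejection rule and the plan does not limit what rejection may be said to show.

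**Conclusion.** The concern holds in a limited form. Under the plan as written, 9 or more of 40 supports a DCR above 15% in the mix enrolled. It does not by itself support activity above the historical rate for those patients, because the source of the 15% and the entry rule differ on prior treatment and nothing aligns them.

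The size cannot be fixed from the documents. Under the assumptions shown, the chance of rejection with no added activity moves from an exact 13.5% to between 19% and 56%. If nearly all enrolled patients are heavily pre-treated, or if background DCR does not vary with prior lines, the effect is small or absent. The point does not show that the 85% power is wrong, that the enrolled patients were in fact less pre-treated, or that case mix explains the interim 33%.

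**What to change.** Keep the 40-patient test. In 14.2 and 14.6:

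1. Pre-specify DCR by number of prior regimens, from the treatment history reviewed under 10.3.1.1, with exact one-sided 90% intervals.
2. Define the heavily pre-treated subset without reference to the outcomes of the 15 patients already treated. Set its estimate beside the 15% benchmark as a sensitivity analysis, with no test.
3. State that rejection in the unrestricted 40 supports only a DCR above 15%, and that activity above the historical control may be claimed only if the matched-subset estimate agrees.
4. Attach the same caveat to the 9 versus 5 month OS comparison.

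The cost is plan wording and one tabulation of data already reviewed, with no new patients or procedures. The downsides are a less precise subset estimate and a narrower permitted claim. For example, at an observed DCR of 30% the exact one-sided 90% lower bound is 20.5% for 12 of 40 but 16.6% for 6 of 20.

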14.6 Efficacy Analysis

Secondary endpoints will be used to gain preliminary estimates of efficacy. The analyses of secondary endpoints will be based on patients enrolled in the expansion cohorts and will be summarized within disease type. ORR will be estimated for each disease cohort and will be summarized with 90% confidence intervals estimated using exact binomial methods. For samples of size 12, the confidence intervals will be no wider than 0.5. Time-to-event endpoints (i.e., PFS, OS, TTP) will be summarized using the product-limit method of Kaplan-Meier; confidence intervals will be based on log(-log(survival)) methodology. Six-month PFS, 12-month OS, and median TTP will be presented, by disease, with 90% confidence intervals. With few patients in each disease, statistical testing will be of low power. Therefore, the analyses within disease will be primarily descriptive and will not rely on p-values.

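### The colorectal disease control test in section 14.2 is labelled single-stage with alpha 0.1 and 85% power, but 15 of its 40 patients had already been observed and had prompted the expansion

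*Combined protocol and SAP*

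**What the plan says.** Section 14.2 describes a look at the colorectal data before the expansion was decided: "We performed an interim analysis of the 15 CRC patients who received the RP2D (3 in the dose escalation and 12 in the dose expansion"). It "observed a response rate of 7% (1 PR), 4 patients (26%) with best RECIST response of stable disease for a median of 10 months". The DCR counts complete or partial response, or "stable disease of at least 6 months duration, was 33" per cent. The section says this activity exceeds a historical DCR of 15%, and gives that as the reason for adding 25 patients.

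The cohort is then to be expanded "with a target sample size of 40 patients (15 already enrolled plus 25 additional"). On the test, the section says: "This will be a single-stage design that will have 85% power to detect a difference in DCR of 15% versus 30" per cent, at one-sided alpha 0.1 by a chi-squared test. The null is rejected at 9 or more of 40. The DCR is to be reported with a one-sided 90% exact confidence interval.

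Three other places bear on this. Section 1.1 gives the initial size of each expansion cohort as 12. DCR appears neither among the secondary objectives in 1.3 nor among the endpoint definitions in 14.5; it is defined only in 14.2. Section 14.6 says that "the analyses within disease will be primarily descriptive and will not rely on p-values".

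**The concern.** A single-stage calculation assumes that the hypotheses, sample size and cut-off are fixed before any of the patients are observed. By the plan's own account, 15 of the 40 outcomes were known when this test was set up, and they were the reason for setting it up. The same 15 patients generate the hypothesis and count toward confirming it. Section 14.2 gives no rule for the look, no conditional error rate, no adjustment and no separate analysis of the 25 new patients.

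This is the only rule in the plan that formally rejects a null for a clinical efficacy endpoint. A reader of the final report would take a rejection as evidence at the 10% level from a test with 85% power, and it would not be that.

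**Working it through.** **Inputs, all from section 14.2.** Null 0.15; alternative 0.30; n = 40 = 15 + 25; one-sided alpha 0.1; reject at 9 or more. Interim count: 1 partial response + 4 stable disease = 5, and 5/15 = 33%, which matches the stated DCR.

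**Step 1: reproduce the plan's figure.** One-sample normal (chi-squared) approximation, no continuity correction:
- Critical count = 40 × 0.15 + 1.2816 × √(40 × 0.15 × 0.85) = 6 + 1.2816 × 2.258 = 8.89, rounded up to 9.
- Size at 9 = P(Z ≥ (9 − 6)/2.258) = P(Z ≥ 1.328) = 0.092.
- Power at 9 = P(Z ≥ (9 − 12)/√(40 × 0.30 × 0.70)) = P(Z ≥ −3/2.898) = 0.850. At 8.89 it is 0.858.

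So 85% and 0.1 reproduce, on two conditions: all 40 patients are unseen, and the approximation is used.

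**Step 2: exact figures for the same rule, still with 40 unseen patients.** With X binomial(40, p):

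| Cut-off | Exact alpha, p = 0.15 | Exact power, p = 0.30 |
|---|---|---|
| ≥ 9/40 | 0.135 | 0.889 |
| ≥ 10/40 | 0.067 | 0.804 |

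The 9/40 rule therefore exceeds an exact 0.10 before the interim look is considered. The exact one-sided 90% lower bound at 9/40 is 14.1%, so the interval the plan promises would not exclude 15% at the count where the rule rejects.

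**Step 3: condition on what was already known.** With 5 in hand, rejection needs 9 − 5 = 4 of the 25 new patients. With Y binomial(25, p):
- P(Y ≥ 4 | p = 0.15) = 0.529.
- P(Y ≥ 4 | p = 0.30) = 0.967.
- A new-patient result of 4/25 = 16%, close to the null, would be enough.
- Expected pooled DCR, if the new patients' true rate is 15% = (5 + 25 × 0.15)/40 = 8.75/40 = 21.9%.

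**Step 4: treat the look as a go/no-go stage.** The plan states no threshold, so s is an assumption shown as a range. Expand if at least s of 15 have disease control, then reject at 9 or more of 40. The unconditional probability of rejecting is Σ over x ≥ s of P(X₁₅ = x) × P(Y ≥ 9 − x).

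| s | Alpha | Power |
|---|---|---|
| 0 (no look) | 0.135 | 0.889 |
| 2 | 0.129 | 0.873 |
| 3 | 0.109 | 0.812 |
| 4 | 0.074 | 0.675 |
| 5 | 0.037 | 0.476 |

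A look that can only stop or continue lowers both columns from the no-look row; it never raises alpha above 0.135.

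**Step 5: a test on the 25 new patients alone.** At ≥ 6/25 exact alpha is 0.162. At ≥ 7/25 exact alpha is 0.070 and power is 0.659, so 7 is the lowest cut-off with exact alpha at or below 0.10.

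**The case against.** The strongest reply is that an interim look with no early rejection cannot inflate the type I error. As a statement about a prespecified rule this is right, and step 4 shows it. A reader might infer from the 0.53 that the procedure's type I error is 53%, or from the step 4 table that the look is what breaks the stated alpha. Neither follows. The 0.53 is a rejection probability given 5/15. The excess over 0.10 in the rows for s = 2 and 3 is inherited from the exact 0.135 of the 9/40 rule and owes nothing to the look. The reply does not rescue the stated figures, though: no go rule was prespecified, so there is no procedure to average over.

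The 21.9% is likewise conditional. Averaged over outcomes that pass a go threshold, the null expectation runs from 16.8% (s = 2) to 22.7% (s = 5), so the upward bias could be smaller under another framing.

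A second reply is that this is a phase Ib trial. The primary objectives in 1.2 are safety, tolerability and the recommended dose; efficacy is preliminary, and the reuse of the 15 patients is disclosed. That limits the severity. It does not justify quoting an alpha and a power, and it favours the descriptive reporting that 14.6 already prescribes.

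A reader might also infer that the denominator is ambiguous, because 14.1 says the secondary analyses "may include those patients in the dose escalation who received the recommended dose and had the same tumor type", while 14.6 refers to the expansion cohorts. For this test the documents do not support that: 14.2 counts the 3 escalation patients explicitly and fixes the denominator at 37 + 3 = 40.

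**Conclusion.** The point holds as a mislabelled test. The stated one-sided alpha of 0.1 and power of 85% describe 40 unseen patients under a normal approximation. The actual test reuses the 15 patients whose results generated its hypothesis. Given their 5/15, it rejects with probability 0.53 at a true DCR of 15% in the new patients and 0.97 at 30%. A separate defect is that 9/40 has exact alpha 0.135 even with no prior look.

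The problem is post hoc reuse of hypothesis-generating data, and should not be described as inflation from a planned interim analysis. The conclusion rests on reading 33% of 15 as 5 patients, which agrees with the listed responses, and on the order of events in 14.2, where the look precedes the expansion and its test. It should be fixed, but it does not touch the trial's primary objectives.

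**What to change.** In section 14.2:
1. Delete the single-stage label, the alpha 0.1 and 85% power claims, and the use of 9/40 as a confirmatory rejection rule.
2. Report the DCR in all 40 patients as a descriptive estimate with its exact interval, in line with 14.6, and state that it includes the 15 patients whose results led to the expansion.
3. Report the DCR with an exact interval in the 25 new patients separately.

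If the sponsor wants to keep a formal test, base it on the 25 new patients only: reject at 7 or more of 25, with exact alpha 0.070 and power 0.66, and state that power in the plan.

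The cost is a wording amendment to the combined protocol and SAP, with no added patients or assessments. The loss is that the trial no longer claims an 85%-powered colorectal test. If the 25-patient test is chosen, it has about a one-in-three chance of missing a true DCR of 30% (1 − 0.66 = 0.34), which is a reason to prefer descriptive reporting alone.

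### The CRC cut-off of 9 of 40 has an exact one-sided type I error of 0.135, not 0.10, and at exactly 9 of 40 it disagrees with the exact interval the plan will report

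*Combined protocol and SAP*

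**What the plan says.** Section 14.2 brings the colorectal (CRC) cohort to 40 patients: 15 already treated at the recommended dose, plus 25 more. It describes the design as follows: "This will be a single-stage design that will have 85% power to detect a difference in DCR of 15% versus 30" percent. The level is one-sided 0.1 and the named test is chi-squared. The decision rule is: "The null DCR of 15% will be rejected if there are 9 or more patients with disease control out of 40 CRC patients". For reporting, "we will present the DCR with a one-sided 90% exact confidence interval".

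The section does not give the exact error rate of the 9-of-40 rule. Neither it nor any other section says whether the rule or the interval governs if they disagree.

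**The concern.** A rejection region that is a fixed count out of 40 has an error rate that can be computed without approximation. The plan instead sets the count by a large-sample test, under a null where 40 × 0.15 = 6 events are expected, and then reports the result with an exact interval. Two things can follow. The real level of the rule can exceed the declared 0.10, and the rule can reject a null value that the accompanying interval retains.

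This is the only powered clinical efficacy test in the trial. If the count lands on the boundary, the report would declare the null rejected next to an interval that includes it, with nothing pre-specified to settle the matter.

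**Working it through.** **Inputs, all from Section 14.2:** n = 40; null DCR p0 = 0.15; alternative p1 = 0.30; one-sided alpha 0.10 (z = 1.2816); reject at X ≥ 9; exact one-sided 90% interval; interim DCR of 33% in 15 patients, which is 5 of 15.

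**1. Reproducing the plan's figures** (one-sample chi-squared test as a normal approximation, no continuity correction)
- Null SD of the count: √(40 × 0.15 × 0.85) = 2.258.
- Critical count: 6 + 1.2816 × 2.258 = 8.89, so the cut-off is 9.
- At 9 of 40: z = (9 − 6)/2.258 = 1.328, one-sided p = 0.092.
- Power: Φ[(0.15√40 − 1.2816√(0.15 × 0.85)) / √(0.30 × 0.70)] = Φ(1.07) = 0.858.

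Both the cut-off and the stated 85% are reproduced. With a continuity correction, z = (8.5 − 6)/2.258 = 1.107 and p = 0.134, so 9 of 40 would not reject.

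**2. Exact properties of each cut-off**, P(X ≥ r) for X ~ Binomial(40, p), with the exact one-sided 90% lower limit at r of 40 (the 0.10 quantile of Beta(r, 41 − r)):

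| Reject at | Type I error (p = 0.15) | Power (p = 0.30) | Lower limit at r/40 |
|---|---|---|---|
| 8 or more | 0.244 | 0.945 | 12.0% |
| 9 or more | 0.135 | 0.889 | 14.1% |
| 10 or more | 0.067 | 0.804 | 16.2% |
| 11 or more | 0.030 | 0.691 | 18.3% |

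The cut-off of 9 misses the alpha target and the cut-off of 10 misses the power target. No cut-off at n = 40 gives both exact alpha ≤ 0.10 and exact power ≥ 0.85.

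**3. Where rule and interval disagree.** The exact lower limit is above 15% only from 10 of 40 upwards. At 8 or fewer neither rejects, and at 10 or more both do. The only conflict is at exactly 9:
- P(X = 9) at p = 0.15: 0.1354 − 0.0672 = 0.068.
- P(X = 9) at p = 0.30: 0.8890 − 0.8041 = 0.085.

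**4. Effect of the 15 patients already seen.** Starting from 5 of 15, the 9-of-40 rule needs 4 of the 25 new patients, and the 10-of-40 rule needs 5. At a true DCR of 15%:
- P(Binomial(25, 0.15) ≥ 4) = 0.53.
- P(Binomial(25, 0.15) ≥ 5) = 0.32.

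**The case against.** The plan names its test, and under that test its numbers are right: step 1 of the working gives the cut-off of 9 and the 85% power. A reader might infer a slip in arithmetic, and the documents do not support that. What stands against the plan is the choice of approximation with 6 expected null events, and its pairing with an exact interval. Naming the test explains the cut-off but does not make the rule's level 0.10. Exact binomial methods are already used for the response-rate intervals in Section 14.6 and for the paired-biopsy test in Section 14.8, so the CRC rule is the exception.

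The stakes are also limited. A reader might infer that this is the trial's only powered test, but Section 14.8 powers a biomarker comparison on paired biopsies. A reader might also infer that the rule settles whether the combination is declared active in CRC, but Section 14.2 attaches no go/no-go action to rejection. The primary objectives in Section 1.2 concern safety, tolerability and dose. DCR is not among the secondary objectives in Section 1.3 or the endpoint definitions in Section 14.5. Section 14.6 treats within-disease analyses as mainly descriptive, though it justifies this by small disease groups, which fits poorly with a powered test in 40 patients. All of this lowers the severity. It does not remove the need for a stated level and cut-off to match.

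Finally, the power discrepancy is in the plan's favour: exact power is 0.889, above the 85% claimed.

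**Conclusion.** The concern holds. Taken on its own, the 9-of-40 rule has exact one-sided type I error 0.135 against a stated 0.10, about 35% higher in relative terms. At exactly 9 of 40 it rejects 15% while the planned interval, with lower limit 14.1%, keeps it. The conflict is confined to that one count and should not be read as a general contradiction between test and interval.

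These figures assume 40 evaluable patients with independent outcomes and no earlier look. The last condition is not met: the 15 patients already analysed are among the 40, and their result prompted the expansion. A reader might therefore take 0.135, or 0.067 after correction, as the false-positive rate of the trial as run. Neither is. Given 5 of 15, the chance of rejecting at a true DCR of 15% is 0.53 with the present rule and 0.32 with a cut-off of 10. Reuse of the interim patients is a separate weakness that changing the cut-off does not cure.

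**What to change.** In Section 14.2, replace the chi-squared test with the exact binomial test, set rejection at 10 or more of 40, and restate the design as exact one-sided alpha 0.067 with exact power 0.80. The exact test at 0.10 and the exact one-sided 90% lower limit then give the same answer at every count.

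Add a sentence saying that these figures treat the 40 patients as a single fresh sample and do not account for the 15 already analysed, and give the conditional figure of 0.32 from 5 of 15.

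The cost is a few sentences and a stated power of 80% instead of 85%, with no extra patients. If 85% must be kept, the smallest sample meeting both targets exactly is 42 with a cut-off of 10 (alpha 0.089, power 0.852), two more evaluable patients; the same caveat on reused patients applies.

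Make the change before the final CRC count is known. If the count is already known, keep the planned rule on record and report its exact error rate beside it, so that the cut-off is not seen to have been chosen after the result.
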